12.2 Masked Dose Escalation Phase

12.2.1 Visit 2: Baseline (Day 1)

The following procedures will be performed at Visit 2, Baseline (Day 1):

- Review inclusion/exclusion criteria
- Review and update medical, surgical, and ocular history
- Review concomitant medications
- Randomization
- Obtain vital signs
- Urine pregnancy test (for women of childbearing potential)
- Blood sample for clinical chemistry, hematology, and coagulation. If screening laboratories were performed ≤ 14 days prior to Baseline (Day 1), these tests do not have to be repeated.
- Urinalysis. If screening laboratories were performed ≤ 14 days prior to Baseline (Day 1), this test does not have to be repeated.
- The following ophthalmic procedures will be performed:
 - NL-BCVA
 - LL-BCVA
 - Slit-lamp bio-microscopy

- IOP
- Gonioscopy
- Dilated ophthalmoscopy
- FA
- Color fundus photographs
- SD-OCT
- Retinal oximetry imaging (may be performed at selected sites)
- Aqueous humor collection (50 µl) from the study eye by paracentesis and shipped the same day on dry ice.
- AEs
- Dispense 1 week supply of masked study drug (5 mg emixustat or placebo) for subjects to self-administer 4 tablets (orally, QD, in the evening) for 7 days.
- Schedule subject to return for Visit 3 (Day 8 ± 1 day).

12.2.2 Visit 3 (Day 8 ± 1 day)

- AEs
- Review concomitant medications
- Collect blister pack of study drug and review compliance
- Dispense a 1 week supply of double the dose received at the Day 1 visit (10 mg emixustat or placebo) for self-administration of 4 tablets (orally, QD, in the evening) for 7 days.

12.2.3 Visit 4 (Day 15 ± 1 day)

- AEs
- Review concomitant medications
- Collect blister pack of study drug and review compliance
- Dispense a 1 week supply of double the dose received at the Day 8 visit (20 mg emixustat or placebo) for self-administration of 4 tablets (orally, QD, in the evening) for 7 days.

Note: Dose reduction is available for subjects who do not tolerate dose escalations due to AEs that in the opinion of the investigator would otherwise lead to discontinuation of study drug. The subject will be returned to and held stable at the last tolerated dose.

12.2.4 Visit 5 (Day 22 ± 1 day)

- AEs
- Review concomitant medications
- Collect blister pack of study drug and review compliance
- Dispense a 1 week supply of double the dose received at the Day 15 visit (40 mg emixustat or placebo) for self-administration of 4 tablets (orally, QD, in the evening) for 7 days.

Note: Dose reduction is available for subjects who do not tolerate dose escalations due to AEs that in the opinion of the investigator would otherwise lead to discontinuation of study drug. The subject will be returned to and held stable at the last tolerated dose.

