	
µl sample of aqueous humor will be collected from the study eye by paracentesis and shipped the same day on dry ice.
 
A one week supply of study drug (5 mg emixustat or placebo) will be dispensed, and subjects will self-administer drug (4 tablets) orally, QD, in the evening for 7 (\pm 1) days. Adverse events (AEs) will be assessed.
 
At Visit 3 (Day 8 \pm 1), subjects return for study drug, review of concomitant medications, and assessment of AEs; each subject will receive a 1 week supply of double the dose received at Visit 2 (10 mg emixustat or placebo), to be dispensed for self-administration, orally, QD (4 tablets) in the evening for 7 days (\pm 1 day).
 
At Visit 4 (Day 15 \pm 1), subjects return for study drug, a review of concomitant medications, and assessment of AEs; each subject will receive a 1 week supply of double the dose received at Visit 3 (20 mg emixustat or placebo), to be dispensed for self-administration, orally, QD, in the evening, for 7 days (\pm 1 day).
 
At Visit 5 (Day 22 \pm 1), subjects return for study drug, a review of concomitant medications, and assessment of AEs; each subject will receive a 1 week supply of double the dose received at Visit 4 (40 mg emixustat or placebo), to be dispensed for self-administration, orally, QD (4 tablets) in the evening for 7 days (\pm 1 day).
 
Subjects who do not tolerate dose escalations due to AEs that, in the opinion of the investigator would otherwise lead to discontinuation of study drug will be returned to and held stable at the last tolerated dose (ie, dose reduction). Dose reduction may only be undertaken once and is only available at Visit 4 (Day 15), Visit 5 (Day 22), or Visit 6 (Day 29).
 
Masked, Fixed Dose Phase: At Visit 6 (Day 29 \pm 1), subjects return for study drug; a review of concomitant medications, urine pregnancy test (for women of childbearing potential), NL-BCVA, ophthalmic exams (slit lamp biomicroscopy, IOP, dilated ophthalmoscopy), SD-OCT, and retinal oximetry imaging (selected sites) will be performed. Each subject will receive a 4-week supply of study drug (40 mg emixustat or the last tolerated emixustat dose; or placebo), to be

--	---

dispensed for self-administration, orally, QD (4 tablets) in the evening for 28 days.

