11.1.3 Dose Reduction

Subjects who do not tolerate dose escalations will be returned to and held stable at the last tolerated dose; after week 4, all subjects will be held at a stable dose for the remainder of the study. Dose reduction is available for subjects who do not tolerate dose escalations due to AEs that in the opinion of the investigator would otherwise lead to discontinuation of study drug. Dose reduction may be undertaken only once and is only available at Visit 4, Visit 5, or Visit 6.

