12.3 Masked, Fixed Dose Phase

12.3.1 Visit 6 (Day 29 ± 1 day)

- Urine pregnancy test (for women of childbearing potential)
- Review concomitant medications
- The following ophthalmic procedures will be performed:
 - NL-BCVA
 - Slit-lamp biomicroscopy
 - IOP
 - Dilated ophthalmoscopy
 - SD-OCT
 - Retinal oximetry imaging (may be performed at selected sites)
- AEs
- Collect blister pack of study drug and review compliance

- Dispense a 4 week supply of drug (40 mg emixustat or the last tolerated emixustat dose; or placebo), to be dispensed by self-administration of 4 tablets (orally, QD, in the evening) for 28 days.

Note: Dose reduction is available for subjects who do not tolerate dose escalations due to AEs that in the opinion of the investigator would otherwise lead to discontinuation of study drug. The subject will be returned to and held stable at the last tolerated dose.

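### The Visit 5 dispensing line lacks the wording for already-reduced subjects that Visits 6 and 7 carry, so for a subject reduced at Visit 4 it conflicts on its face with the hold rule

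*Combined protocol and SAP*

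**What the plan says.** The general rule is in section 11.1.3: "Subjects who do not tolerate dose escalations will be returned to and held stable at the last tolerated dose". The same section limits its use: "Dose reduction may be undertaken only once and is only available at Visit 4, Visit 5, or Visit 6". The Note in section 12.2.3 applies the rule at Visit 4: "The subject will be returned to and held stable at the last tolerated dose". The Protocol Summary states it straight after its Visit 5 text: such subjects "will be returned to and held stable at the last tolerated dose (ie, dose reduction").

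The Visit 5 dispensing line in section 12.2.4 reads: "Dispense a 1 week supply of double the dose received at the Day 15 visit (40 mg emixustat or placebo"). The Protocol Summary (Study Procedures) has: "each subject will receive a 1 week supply of double the dose received at Visit 4 (40 mg emixustat or placebo"). Neither line qualifies the doubling. The Note under the 12.2.4 line says that reduction is available for subjects who do not tolerate escalation, and repeats that they are returned to and kept at the dose last tolerated.

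The Visit 6 line in section 12.3.1 is worded differently: "Dispense a 4 week supply of drug (40 mg emixustat or the last tolerated emixustat dose; or placebo"). The Visit 7 line in section 12.3.2 carries the same alternative. Section 11.1.1 lists Weeks 4 to 12 as 40 mg/day without qualification.

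**The concern.** A subject reduced at Visit 4 is to be held at the lower dose, yet the next dispensing line that applies to that subject says to double. The line that site staff work from and the rule that governs the subject do not match.

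If the line were followed literally, the subject would go back up after adverse events that, in the investigator's opinion, would otherwise have led to stopping study drug. Section 11.1.3 allows one reduction only, so it could not be used again. Under section 9.6 a subject who stops treatment early is withdrawn from the study, and section 9.6.2 rules out replacement. Dispensing is masked and resupply kits come through the IWRS (section 10.2), so a site may not be able to tell from the tablets that the dose has risen.

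**Working it through.** No sample-size or power figure enters this point. The check is the dose ladder and a comparison of the texts.

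**Inputs.** Starting dose 5 mg (section 11.1.1, Week 1); doubling at Visits 3, 4 and 5 (sections 12.2.2 to 12.2.4); one reduction, at Visit 4, 5 or 6 (section 11.1.3).

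**Reproducing the plan's figure.** 5 mg at Visit 2; 2 × 5 = 10 mg at Visit 3; 2 × 10 = 20 mg at Visit 4; 2 × 20 = 40 mg at Visit 5. The 40 mg in the Visit 5 line is therefore the nominal ladder value for a subject who has never been reduced. For that subject the line is consistent.

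**A subject reduced at Visit 4.** The subject took 10 mg in Week 2, did not tolerate it, and is returned to 5 mg. At Visit 5:

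- the hold rule (11.1.3, the Note in 12.2.3, the Protocol Summary) gives 5 mg;
- doubling the Day 15 dose, taken literally, gives 2 × 5 = 10 mg, the dose not tolerated;
- the figure in parentheses, 40 mg, no longer equals double the dose received, so the line does not fit this subject.

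**Which reductions meet the gap.**

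| Reduced at | Change | Next dispensing line | Provides for a reduced subject? |
|---|---|---|---|
| Visit 4 | 10 to 5 mg | Visit 5 (12.2.4) | No |
| Visit 5 | 20 to 10 mg | Visit 6 (12.3.1) | Yes |
| Visit 6 | 40 to 20 mg | Visit 7 (12.3.2) | Yes |

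Only a Visit 4 reduction is followed by an unqualified doubling.

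**Whether the Visit 5 Note closes the gap.** It offers reduction to subjects who do not tolerate escalation. It does not say what to dispense to someone who has already used the one reduction. Visit 6 has the same Note and also carries the alternative in the dispensing line; Visit 5 has the Note alone.

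**Aqueous sampling after early termination.** Section 12.5 omits the sample only if study drug was received for fewer than 21 days. Visit 5 falls on Day 22 ± 1, so Day 21 at the earliest. With one evening dose daily from Day 1 and none missed, 20 doses precede a Day 21 visit, and the first dose from the Visit 5 supply is the 21st. A subject stopping at a Day 29 visit has had 28. A sample is therefore still called for, though before Day 85.

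**The case against.** The strongest reply is that the intended design is clear. The hold rule appears in the Protocol Summary (three times), in sections 6.3, 8.1 and 11.1.3, and in the Notes at Visits 4, 5 and 6. Holding a dose stable means little if it doubles a week later. The Visit 4 section has the same form, with the nominal step in the line and the exception in the Note. Section 11.1.1 is the nominal schedule, and 11.1.3 sits under the same heading. Section 8.1 puts the 40 mg statement and the hold rule in consecutive sentences.

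Most of this stands, and it limits the point. A reader might infer that the protocol makes no exception and requires re-escalation; the repeated hold rule does not support that. A reader might also treat 5, 10 and 40 mg as three rival instructions and quote an eightfold range, but 40 mg is only the nominal ladder value. It would be tempting, too, to say that the IWRS will issue the wrong kits. Section 10.2 says only that resupply kits come through the IWRS; how kits are assigned is not shown.

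What the reply does not remove is the contrast with Visits 6 and 7. The exception was written into those dispensing lines and not into the Visit 5 line, and that is the one visit where its absence matters.

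**Conclusion.** The point holds as a drafting conflict with a conditional safety consequence. The Visit 5 line and its Protocol Summary counterpart, read literally, contradict the hold rule for a subject reduced at Visit 4, and the Visit 5 Note leaves that subject's position unstated. Re-exposure depends on the line being applied without the hold rule; a reader of the whole protocol would probably not do that.

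The size cannot be given as a number. The documents state no expected rate of intolerance. The affected group is limited to emixustat subjects reduced at Visit 4, out of a planned 10 in that arm, and could be empty. Placebo subjects may be mock-reduced but receive 0 mg on any reading.

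A reader might infer that a resulting withdrawal forfeits the aqueous sample, or uses up half of the two extra subjects planned per arm. The first is not supported: after at least 21 days of drug, section 12.5 still calls for a sample at Early Termination, so what is lost is the Day 85 timing. The second assumes that the event occurs, and nothing in the documents says that it will.

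The point is worth correcting because it concerns an operational dosing instruction and the correction is small. No view is taken here on which dose is right.

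**What to change.** Reconcile the Visit 5 dispensing line in section 12.2.4, the matching Protocol Summary text and the Weeks 4 to 12 entry in section 11.1.1 with section 11.1.3 and the Visit 4 Note in section 12.2.3. The Visit 5 line should state one instruction for a subject whose dose has already been reduced, as the Visit 6 and 7 lines do. The sponsor must decide which instruction stands. Then check that the IWRS kit-assignment rule matches it.

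The cost is a line of wording in each affected place and one specification check. It needs no extra visits, subjects or tablet strengths.

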12.3 Masked, Fixed Dose Phase

12.3.1 Visit 6 (Day 29 ± 1 day)

- Urine pregnancy test (for women of childbearing potential)
- Review concomitant medications
- The following ophthalmic procedures will be performed:
 - NL-BCVA
 - Slit-lamp biomicroscopy
 - IOP
 - Dilated ophthalmoscopy
 - SD-OCT
 - Retinal oximetry imaging (may be performed at selected sites)
- AEs
- Collect blister pack of study drug and review compliance

- Dispense a 4 week supply of drug (40 mg emixustat or the last tolerated emixustat dose; or placebo), to be dispensed by self-administration of 4 tablets (orally, QD, in the evening) for 28 days.

Note: Dose reduction is available for subjects who do not tolerate dose escalations due to AEs that in the opinion of the investigator would otherwise lead to discontinuation of study drug. The subject will be returned to and held stable at the last tolerated dose.

12.3.2 Visit 7 (Day 57 ± 5 days)

- Urine pregnancy test (for women of childbearing potential)
- Review concomitant medications
- The following ophthalmic procedures will be performed:
 - NL-BCVA
 - Slit-lamp biomicroscopy
 - IOP
 - Dilated ophthalmoscopy
 - SD-OCT
 - Retinal oximetry imaging (may be performed at selected sites)
- AEs
- Collect blister packs of study drug and review compliance
- Dispense a 4 week supply of drug (40 mg emixustat or the last tolerated emixustat dose; or placebo), to be dispensed by self-administration of 4 tablets (orally, QD, in the evening) for 28 days.

12.3.3 Visit 8 (Day 85 ± 5 days)

- Review concomitant medications
- Collect blister packs of study drug and review compliance
- Urine pregnancy test (for women of childbearing potential)
- Physical exam including weight
- Vital signs
- Blood samples for clinical chemistry, hematology (including HbA1c), and coagulation

- Urinalysis
- 12-lead ECG
- The following ophthalmic procedures will be performed:
 - NL-BCVA
 - LL-BCVA
 - Slit-lamp biomicroscopy
 - IOP
 - Gonioscopy
 - Dilated ophthalmoscopy
 - FA
 - Color fundus photography
 - SD-OCT
 - Retinal oximetry imaging (may be performed at selected sites)
- Aqueous humor collection (50 µl) from the study eye by paracentesis and shipped the same day on dry ice.
- AEs

12.4 Study Exit

A Study Exit visit will be performed 30 days (\pm 5 days) after the last dose of study drug.

- Review concomitant medications
- Urine pregnancy test (for women of childbearing potential)
- The following ophthalmic procedures will be performed:
 - NL-BCVA
 - Slit-lamp biomicroscopy
 - IOP
 - Dilated ophthalmoscopy
 - SD-OCT

12.5 Early Termination

Subjects who discontinue from the study early will undergo an Early Termination visit where all Day 85 visit assessments will be performed when study drug is stopped, or as soon as possible after stopping study drug; they will then undergo study exit visit evaluations 30 days after the last study drug dose. Subjects who have received study drug <21 days will not undergo collection of an aqueous humor sample at the Early Termination visit. If the Early Termination visit occurs ≥ 25 days after last study drug dose, the Early Termination and Study Exit visits may be combined.

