6.3 Rationale for Dose Selection

To evaluate the effect of visual cycle modulation on aqueous humor biomarkers in subjects with PDR, doses within the range previously assessed for safety have been selected. A once-daily schedule for administration of emixustat has been chosen for this study based on the pharmacokinetic profile characterized in the Phase 1 program (20). Following multiple dosing in healthy subjects who received doses ranging from 5 to 40 mg of emixustat once daily (QD) for 14 days, emixustat was steadily eliminated with terminal elimination half-life values ranging from 4.6 to 7.9 hours. Pharmacokinetic values were similar on Days 1 and 14, with mean accumulation ratio for area under the concentration curve values ranging from 1.04 to 1.19 across across the 10 mg to 40 mg cohorts, indicating no accumulation following QD dosing with emixustat for 14 days. A step-wise dose escalation regimen will be used to evaluate the safety of, and tolerability to, dosing durations longer than 2 weeks. Subjects will be treated for a total of 84 days. Subjects assigned to the emixustat arm will receive 5 mg daily oral emixustat for the first week, then the dose will be doubled on a weekly basis to 10 mg (week 2), 20 mg (week 3), and 40 mg (week 4). Subjects who do not tolerate dose escalations

will be returned to and held stable at the last tolerated dose; after week 4, all subjects will be held at a stable dose for the remainder of the study.

7 Study Objectives

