11.5 Prior and Concomitant Therapy

In addition to the exclusion criteria, the following are excluded during the course of the study:

- Systemic use of a strong inducer of or a strong or moderate inhibitor of CYP2D6 (as listed in [Appendix B](#))
- Anti-coagulant therapy (eg, heparins, warfarin, other oral anti-coagulants). Anti-platelet therapy (eg, aspirin, clopidogrel) is allowed.
- Systemic anti-VEGF or pro-VEGF treatment

If elective, urgent, or emergency surgery is required at any time between randomization and Day 85, the investigator will confer with the Medical Monitor, who will determine if a temporary discontinuation of masked study drug is warranted before and/or after the surgery.

For subjects who undergo ocular treatments, procedures or surgeries (eg, retinal detachment surgery) with the potential to affect protocol assessments or disease outcomes, the Investigator should confer with the Medical Monitor to determine whether or not the subject should continue with study drug.

The Medical Monitor should be notified before prohibited medication or therapy (as listed in [Section 9.3](#) Exclusion Criteria and [Appendix B](#)) is administered unless the safety of the subject requires immediate action. The decision to administer a prohibited medication or therapy should be done with the safety of the subject as the primary consideration. The Medical Monitor will determine whether or not the subject may continue with study participation. The Investigator should contact the Medical Monitor if permissibility of a specific medication or therapy is in question to discuss whether or not the subject should continue with study participation.

12 Study Visits

The Schedule of Events is presented in [Appendix A](#). A detailed accounting of assessments performed at each study visit is presented below.

The scheduled visits include Screening (within 30 days prior to baseline), Baseline (Day 1), and days 8, 15, 22, and 29 (each ± 1 day) and days 57 and 85 (each ± 5 days). The Day 85 visit will be one day after the last drug/placebo treatment. The Study Exit visit will be performed 30 days (± 5 days) after the last dose of study drug.

12.1 Visit 1: Screening (≤ 30 days prior to Baseline [Day 1]):

The following procedures will be performed at Visit 1, Screening (≤ 30 days prior to Baseline [Day 1]):

- Explain the purpose and conduct of the study visits to the subjects, answer the subject's questions, and obtain written informed consent

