15.1 Primary Efficacy Endpoint

The primary study endpoints are the change in aqueous humor concentration of eight biomarkers (IL-6, IL-8, IP-10, PDGF-AA, TGF β -1, MCP-1 and IL-1 β , and VEGF) from baseline (Day 1) to Day 85, the conclusion of an 84-day course of study drug. Analysis will include both absolute change and percent change from Baseline (Visit 2/Day 1) to Day 85 (Visit 8/Study Exit).

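### The Early Termination rule limits the second aqueous tap by time on drug but not by time off drug, so it still calls for a tap 25 or more days after the last dose

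*Combined protocol and SAP*

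**What the plan says.** Section 12.5 sends every early leaver to an Early Termination visit at which "all Day 85 visit assessments will be performed when study drug is stopped, or as soon as possible after stopping study drug". The Day 85 list in Section 12.3.3 includes the tap: "Aqueous humor collection (50 µl) from the study eye by paracentesis and shipped the same day on dry ice". Appendix A agrees, because Visit 8 and Early Termination share one column.

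The only exemption from the tap concerns exposure: "Subjects who have received study drug <21 days will not undergo collection of an aqueous humor sample at the Early Termination visit". The next sentence deals with late attendance: "If the Early Termination visit occurs ≥ 25 days after last study drug dose, the Early Termination and Study Exit visits may be combined". It merges two visits and does not mention the tap. The synopsis and Appendix A footnote a carry the same rules.

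The planned second sample is tied to the end of dosing. Section 12 says: "The Day 85 visit will be one day after the last drug/placebo treatment". Section 15.1 defines the primary endpoint as the change "from baseline (Day 1) to Day 85, the conclusion of an 84-day course of study drug". Study Exit (Section 12.4), 30 ± 5 days after the last dose, has no aqueous collection.

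Section 16 does not say whether an aqueous sample from Early Termination enters the Day 85 comparison.

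**The concern.** The tap rule asks whether the subject has had enough drug. It does not ask whether the subject is still on drug, or recently was. Read literally, someone treated for 21 days or more who stops and comes back four weeks later has a needle procedure in the study eye, taken for research, at an interval that does not match the endpoint sample.

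Two things are at stake. The first is an invasive procedure whose result has no stated use. The second is that the value could enter the primary comparison as if it were a Day 85 value. If the biomarker effect had faded by then, that would pull the emixustat mean towards placebo.

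The visit schedule makes the case possible. Visits 6, 7 and 8 are 28 days apart. A subject whose last dose is on Day 30, and whose stopping comes to light at Visit 7 on Day 57, is 57 − 30 = 27 days off drug with more than 21 days of exposure. The contact procedure in Section 9.6.1 allows two weeks of calls and then a letter, so a late return is plausible. Section 9.6 withdraws everyone who stops treatment early, so the Early Termination rules apply to all of them.

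**Working it through.** **The plan's own power figure.** Section 16 gives 8 per arm, effect size 1.31 SD, a two-sample t-test and two-sided alpha 0.10. The noncentrality is d / √(1/n₁ + 1/n₂) = 1.31 / √(2/8) = 2.62 on 14 degrees of freedom. Exact noncentral-t power is 80.1%, which matches the stated 80%. Allowing for 20% loss, 8 / 0.8 = 10 per arm, which is the number enrolled.

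**Drug remaining.** Section 6.3 reports that "emixustat was steadily eliminated with terminal elimination half-life values ranging from 4.6 to 7.9 hours", with pharmacokinetics "indicating no accumulation following QD dosing with emixustat for 14 days". Half-lives elapsed = days × 24 / half-life; fraction remaining = 2 to the power of minus that number.

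| Time off drug | At 7.9 h | At 4.6 h |
|---|---|---|
| 1 day (24 h) | 24/7.9 = 3.0 half-lives, about 12% left | 24/4.6 = 5.2, about 3% left |
| 25 days (600 h) | 600/7.9 = 76, about 1e-23 left | 600/4.6 = 130, about 5e-40 left |

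For practical purposes no drug is left at 25 days. This describes the drug in healthy subjects after 14 days of dosing. It does not describe the biomarkers.

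**Effect on the comparison if late samples are analysed as Day 85.** Two assumptions are needed, and the documents give neither: a late emixustat sample carries zero effect, and it is entered as a Day 85 value. With 10 per arm and k such samples in the emixustat arm, the mean effect is 1.31 × (10 − k)/10. Power with the samples kept comes from 100,000 simulated t-tests at two-sided alpha 0.10. Power with them left out is exact noncentral-t with 10 − k against 10.

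| k | Mean effect if kept | Power if kept | Power if left out |
|---|---|---|---|
| 0 | 1.31 SD | 87.9% (exact) | 87.9% |
| 1 | 1.31 × 0.9 = 1.18 SD | about 79% | 86.2% (9 vs 10) |
| 2 | 1.31 × 0.8 = 1.05 SD | about 69% | 84.1% (8 vs 10) |

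Under these assumptions, including a late sample costs more power than not having it. A late placebo sample has no drug effect to lose, so the dilution comes only from the emixustat arm.

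**The case against.** The strongest reply is that the late tap is a fallback. Section 12.5 places the visit at drug stop or as soon as possible afterwards, and Section 11.1.4 puts Early Termination assessments before any rescue therapy. Only a subject who stops and then stays away for weeks is affected, and nothing in the documents says how often that would happen. This stands, and it limits the weight of the point.

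A reader might go further in several directions that the documents do not support:

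- **That a sample 25 days off drug cannot show a treatment effect.** The half-life measures drug clearance, not biomarker recovery. No offset time is given, and Section 6.2 says the association of visual cycle modulation with these biomarkers is not known. The planned sample is itself taken 3 to 5 half-lives after the last dose, so the design already relies on an effect that outlasts most of the drug.
- **That each late subject removes one eighth of the effect.** The 8 per arm are those left after early terminations. Ten are enrolled, so tenths are the right unit. One such sample then leaves power near the planned 80%, and two would require both of the emixustat arm's allowed early terminators to return late after 21 or more days on drug.
- **That the lack of a tap at Study Exit shows the protocol regards that time as uninformative.** Completers have already had their second tap at Visit 8. Sparing them a third shows little.
- **That the primary analysis is biased.** No rule carries Early Termination samples into the Day 85 comparison. The bias depends on a choice the plan leaves open, and off-drug data could serve a sensitivity analysis if one were specified.

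**Conclusion.** The gap in the text is real, and closing it is a cheap improvement. As written, a subject with at least 21 days of drug who attends Early Termination 25 or more days after the last dose has the second paracentesis. Essentially no drug remains by then. The result cannot be interpreted as the planned measurement one day after dosing, although a persisting biomarker effect is not ruled out.

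The possible harm to the comparison is conditional. With 10 per arm, zero effect in the late sample and its use as a Day 85 value, one such emixustat subject takes the mean effect to about 1.18 SD and power from about 88% to 79%. Two take it to about 1.05 SD and 69%. Leaving the samples out keeps about 86% and 84%, but then the tap had no stated analytic use. Both the frequency of late visits and the biomarker offset are unknown, so these figures illustrate a range and do not predict a loss.

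**What to change.** In Section 12.5, the Early Termination paragraph of the synopsis and Appendix A footnote a, add that aqueous humor is not collected at a combined Early Termination/Study Exit visit, that is, 25 or more days after the last dose. Stating the interval matters because merging the visits is optional. Keep the non-invasive Day 85 assessments at that visit. Record days since last dose with every aqueous sample, so that any off-drug value can be identified.

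A shorter time-off-drug limit is for the sponsor to justify. Borrowing 5 days from the Visit 8 window would be arbitrary. That window concerns the visit date, and 120 h is already 120/7.9 = 15 to 120/4.6 = 26 half-lives.

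The cost is one sentence in three places and one recorded item. The downside is the loss of an occasional late, off-drug sample for which the plan states no use.
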